NCT04287517 17.03.2020

Efficacy of Capacitive-Resistive Therapy on the Treatment of Myofascial Pain

Study Protocol and Statistical Analysis Plan

NCT04287517 17.03.2020

Material and Methods

Thirty six volunteers with active myofascial trigger points in the upper trapezius and neck were included the study after being examined by sports medicine specialists between 12 December – 1 March. During the examination, the reproduction of the daily life complaints and the presence of a tense muscle band, hypersensitive point, which was characterized by reflected pain and local twitch findings, was evaluated diagnostically. Exclusion criteria were fibromyalgia, discal hernia, radiculopathy, myelopathy, having received trigger point injection and physical therapy within the last 1 month, neck or back surgery, rheumatismal diseases, pregnancy. The study was approved by the Istanbul Faculty of Medicine Ethics Committee. All participants were informed of the study and signed written informed consent. The study was designed as a prospective, randomized, placebo-controlled double-blind trial (NCT04287517). The patients were divided into two groups by a physician who did not participate in patient evaluation using the block randomization method. The Sports Physician who made the evaluations carried out blindly until all data was collected. Patients likewise received their treatment blindly at different times throughout the entire study. The entire randomization process was carried out in accordance with Consort Statement.

Treatment

After the patients were divided into two groups, capacitive resistive therapy and exercise were applied to one group, and placebo (sham) therapy and exercise were applied to the other group by an experienced physiotherapist for 10 sessions. The sessions were continued for 3 weeks with an interval of 24-48 hours. All sessions were planned for 16 minutes (8 minutes to one side and 8 minutes to the other). Individuals who received a placebo treatment were administered sham in empty mode without energy transfer. The patients were reported not to understand that they received a placebo they were working without heating the system. In each session ten minutes capacitive mode six minutes resistive mode was used. Since myosfacial trigger points are predominantly located in superficial muscle tissue, capacitive therapy was preferred. It was also benefited from resistive treatment to achieve deep tissue effect. Physiotherapist after applying capacitive and resistive therapy or placebo to patients; The patients performed neck stretching exercises (for Trapezius and Levator Scapula muscles) and isometric neck exercises 10 repetitions and 3 sets. Each exercise was carried out under the supervision of the same physiotherapist, after each session.

Outcomes

Visual Analog Scale (VAS), neck disability index (NDI), short form - 36 (SF-36) questionnaire, ROM and algometer, Pain Pressure Threshold (PPT), were evaluated blindly by an experienced sports medicine clinician before and after the treatment. In each evaluation, all measurements were repeated 3 times and their averages were calculated at the end. VAS, SF-36 and Neck Disability Index were filled under supervision before each individual started treatment. Subsequently, neck range of motion (ROM) measurement were performed with inclinometer and Pain Pressure Threshold measurement were performed with the algometer.

Pain intensity was evaluated by VAS and Algometer. VAS: A tool used to help a person rate the intensity of certain sensations and feelings, such as pain. The visual analog scale for pain is a straight line with one end meaning no pain and the other end meaning the worst pain imaginable. A patient marks a point on the line that matches the amount of pain he or she feels. The most simple VAS is a straight horizontal line of fixed length, usually 100 mm. The ends

NCT04287517 17.03.2020

are defined as the extreme limits of the parameter to be measured (symptom, pain, health; in this study pain will be studied) orientated from the left (worst) to the right (best). Lower scores mean better outcome. The validity and reliability study of the scale was determined by Price et al. It has a good degree of validity and reliability. PPT is defined as the minimum force applied which induces pain. This measure has proven to be commonly useful in evaluating tenderness symptom. It has been shown to be a reliable method of evaluating myofascial trigger points. Studies have shown high consistency among clinicians (ICC 0.80 - 0.92).

NDI was used for neck disability assessment. Vernon et al. developed NDI as the neck version of Oswestry Low Back Pain Scale. Turkish version of the study was made by Aslan et al. The test-retest reliability value of the questionnaire was found ICC: 0.979 (excellent). Neck Disability Index (NDI) is a self-report questionnaire used to determine how neck pain affects a patient's daily life and to assess the self-rated disability of patients with neck pain. Each question has six statement, the first statement is marked the section score = 0, if the last statement is marked it = 5. Maximum score is 50 and minimum is 0. Lower scores mean better outcome.

The Short Form (36) Health Survey is a 36-item, patient-reported survey of patient health. The SF-36 is a measure of health status and an abbreviated variant of it. The SF-36 consists of eight scaled scores, which are the weighted sums of the questions in their section. Each scale is directly transformed into a 0-100 scale on the assumption that each question carries equal weight. The lower the score the more disability. The higher the score the less disability i.e., a score of zero is equivalent to maximum disability and a score of 100 is equivalent to no disability.

Normal joint movements of the cervical region are important for many activities in daily life. In our study, inclinometer was preferred for the evaluation of cROM. Evaluation of passive joint movements in the cervical region is also used to determine the capsular pattern and final sensation of the joint. In the previous study, the ICC value was found to be 0.89 - 0.94 with the inclinometer. Flexion, extension, lateral rotation in both directions and flexion ROM examinations were performed. The normal cervical spine's range of motion is approximately 80° to 90° of flexion, 70° of extension, 20° to 45° of lateral flexion, and up to 90° of rotation to both sides.

Statistical Analysis Plan

Average values were compared statistically. Evaluations were made both within the group before and after treatment (TO) and also for intergroup before and after treatment. Descriptive statistics of the numerical variables in the study are given as mean, median, min-max, standard standard deviation. Descriptive statistics for categorical variables were given as numbers and percentages. Numerical variables were analyzed with the Shapiro Wilk test. Student t Test was used for group comparison of variables with normal distribution, and Mann Whitney U test was used for group comparisons of non-normally distributed variables. For dependent groups, Paired t Test was used for mean comparisons and Wilcoxon test was used for median comparisons. In calculations, 0.05 was taken as the level of significance. SPSS (version 21) package program was used in the analysis.

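### Does a sham without energy transfer, with no recorded check of participant blinding, undermine the double-blind claim enough to change the plan?

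*Combined protocol and SAP*

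**What the plan says.** Under Material and Methods the design is given as follows: "The study was designed as a prospective, randomized, placebo-controlled double-blind trial". The same paragraph says who was blind. For the assessor: "The Sports Physician who made the evaluations carried out blindly until all data was collected". For the participants, without distinction of arm: "Patients likewise received their treatment blindly at different times throughout the entire study". Allocation was made by a physician who took no part in evaluation.

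Under Treatment, the sham is described thus: "Individuals who received a placebo treatment were administered sham in empty mode without energy transfer". The next sentence is the only remark on whether the sham was noticed: "The patients were reported not to understand that they received a placebo they were working without heating the system". Each course was 10 sessions of 16 minutes, delivered by a physiotherapist who also supervised the exercises and who is not described as blinded.

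Under Outcomes, VAS, NDI and SF-36 are completed by the patient, pressure pain threshold is the force at which pain is induced, and ROM is read from an inclinometer. The Statistical Analysis Plan lists t, Mann-Whitney, paired t and Wilcoxon tests at 0.05. It lists no blinding index or treatment-guess analysis.

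**The concern.** A sham that transfers no energy may feel different from the active treatment, and participants had 10 sessions in which to notice. The protocol itself brings up heating when it explains why placebo recipients were unaware. Its reassurance concerns those recipients only. If the active arm recognised its treatment by warmth, that alone would create a difference in expectation between the arms, even with every sham patient fully deceived.

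Blinding the assessor does not protect outcomes that the participant supplies. VAS, NDI, SF-36 and pressure pain threshold are exposed, and ROM less so. At stake is the purpose of the sham: if expectation differs by arm, a between-group difference on those outcomes cannot be credited to the device. The claim of participant blinding would then be asserted where the design gives some reason to doubt it.

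**Working it through.** The plan states no power, effect size or SD, so there is no figure of its own to reproduce. Four checks bear on the question.

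**1. What the text establishes about warmth.** Only the absence of energy transfer in the sham is clear. The sentence on heating is garbled and allows two readings:
- the sham alone ran without heat, so warmth could identify the active arm;
- the system was worked without heating in general, which would remove warmth as a cue.

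Nowhere do the documents say that active patients felt warmth. Preferring the first reading as fact would need outside knowledge of the device. The treatments may differ in a noticeable sensation; the documents do not show that they do. Nor is the placebo sentence the only support for participant blinding, since Material and Methods asserts it for patients in general and gives one measure, treatment at different times, which limits comparison between patients.

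**2. How much an expectation difference could matter.** Inputs: total of 36 (Material and Methods); 18 per arm (assumed, as arm sizes are not given); level 0.05 (Statistical Analysis Plan), taken as two-sided; true device effect zero; expectation shift of *b* SD (assumed, as the documents give none).

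Noncentrality = *b* × √(18/2) = 3*b*, with 34 degrees of freedom and critical value 2.032.

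| *b* (SD) | 3*b* | Probability of p < 0.05 |
|---|---|---|
| 0.2 | 0.6 | 0.090 |
| 0.3 | 0.9 | 0.141 |
| 0.4 | 1.2 | 0.215 |

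A 16/20 or 14/22 split changes each of these by less than 0.01. The inflation would matter if such a shift existed. But the same table applies to any bias of that size in any two-arm trial of 36, so it is no evidence that a bias occurred here.

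**3. What a treatment-guess question would yield.** With 18 per arm and 50% guessing correctly, the 95% half-width is 1.96 × √(0.5 × 0.5 / 18) = 0.23. On a per-arm index of the form 2*p* − 1 it doubles to 0.46. Only gross unblinding would show.

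A rule that withdraws the label when the active arm guesses correctly more often than chance also misfires. Suppose blinding is perfect and 70% of both arms guess active, whatever they received. For the active arm, X ~ Binomial(18, 0.7):
- P(X ≥ 10), more than half correct: 0.94;
- P(X ≥ 13), the one-sided 5% binomial cut-off (0.048 at *p* = 0.5): 0.53.

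At 60% guessing active, these are 0.74 and 0.21. The label would often be withdrawn with no unblinding at all. A guess taken after treatment also reflects improvement, so an effective device would tend to trigger the rule too.

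**4. Timing.** Inclusion ran from 12 December to 1 March, treatment lasted 3 weeks, and the document is dated 17.03.2020. If the window is 2019–20 and treatment began on inclusion, anyone included by 25 February had finished by that date (25 February + 21 days = 17 March). That covers 75 of the 80 days from 12 December to 1 March. A new question could reach only the last entrants.

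**The case for a change.** The best case for acting is that the remedy costs almost nothing: one question and one table, or, if visits are over, a sentence saying that the success of participant blinding was not assessed. Four of the five outcomes listed (VAS, NDI, SF-36 and pressure pain threshold) rest on the participant's report. The person delivering treatment is not said to be blind and was present at every session. The statement about placebo recipients has no source, method or count, and it cannot speak for the active arm. Treating patients at different times limits contact between them but hides no sensation.

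Much of this stands. The basis of the placebo statement is undescribed, the heating sentence is unclear, and readers should interpret the participant-reported outcomes with that in mind. The missing account is still not evidence that patients knew their allocation. The protocol names the two blinded parties, patients and evaluator, and makes no claim for the physiotherapist, so the double-blind label is not contradicted by its own text. A guess question would measure blinding poorly and too late, and it would correct no estimate. Rewording the label would change no analysis and no result.

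**Conclusion.** No change to the plan follows. The documents assert blinding of patients and evaluator and contain nothing that shows the assertion to be false. Differential warmth is one reading of an unclear sentence. The rejection rates of 9% to 21% rest on assumed shifts of 0.2 to 0.4 SD, 18 per arm and a two-sided test; they show what unblinding could do and say nothing of whether it happened. A blinding check at this size would have a half-width of about 0.23 per arm at 50% correct, would be confounded with benefit, and would miss most participants.

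The gap is one of description, and authors would ordinarily fill it when writing up: whether heat was present in each arm, how the placebo patients' belief was learned, and, failing that, a stated limitation for VAS, NDI, SF-36 and pressure pain threshold. Using a silent device as sham, with patients and evaluator blind, is a fair trade-off for a trial of 36. The conclusion would differ if the documents showed that active patients felt heat which sham patients did not, or recorded that patients had identified their treatment.

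### Does placing worst pain on the left of the VAS line contradict the rule that lower scores are better?

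*Combined protocol and SAP*

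**What the plan says.** The VAS paragraph of the Outcomes section opens with the purpose, "Pain intensity was evaluated by VAS and Algometer", and describes the instrument as "a straight line with one end meaning no pain and the other end meaning the worst pain imaginable". That sentence does not assign either anchor to the left or the right. The paragraph goes on: "A patient marks a point on the line that matches the amount of pain he or she feels", and then "The most simple VAS is a straight horizontal line of fixed length, usually 100 mm". The last sentence is a general remark about the simplest kind of VAS, and the length of the form used in this trial is not given. The same general description then sets the direction of the line and of the score: "orientated from the left (worst) to the right (best). Lower scores mean better outcome". A parenthesis in the orientation sentence lists several constructs that such a line can measure and notes that pain is the one studied here.

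The document does not name the end from which the distance to the mark is taken, and it does not mention reversing the score. The Statistical Analysis Plan section compares groups with the t test or Mann-Whitney U test, and before with after by the paired t test or Wilcoxon test. The significance level is 0.05, with sidedness not stated.

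**The concern.** Many readers assume that a horizontal scale is measured from its left end. With worst pain on the left, that habit gives the lowest number to the worst pain, and the next sentence says the opposite. Two adjacent sentences then appear to conflict.

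The VAS is the only patient-rated measure that the plan assigns to pain intensity, in a trial whose subject is myofascial pain. If all forms were scored from the wrong end, a benefit would be reported as a harm. If only some were, the group difference would be diluted and its variance inflated. The direction cannot be borrowed from the other questionnaires either, because on the NDI lower is better and on the SF-36 higher is better.

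**Working it through.** The plan gives no figure on this point to reproduce. The check concerns direction, followed by the consequences of a wrong reading.

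**Inputs**

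- Orientation (Outcomes): worst at the left, best at the right.
- Scoring direction (Outcomes): "Lower scores mean better outcome".
- Line length L: 100 mm, an assumption taken from the general description.
- Measuring end: not stated.
- Participants: 36 (Material and Methods). Assessments: 2, before and after treatment (Outcomes). Repeats per assessment: 3 (Outcomes).
- Tests: those of the Statistical Analysis Plan section, taken as two-sided (assumption).

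**Step 1: which origin fits the text?** Let x be the distance of the mark from the left end. The two candidate scores are s_left = x and s_right = L - x.

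| Mark | s_left | s_right |
|---|---|---|
| Left end (worst pain), x = 0 | 0 | 100 |
| x = 30 | 30 | 70 |
| Right end (no pain), x = 100 | 100 | 0 |

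Under s_left, higher is better, against the stated rule. Under s_right, lower is better, as stated. Of the two origins only the right-hand one satisfies both sentences, so the text determines the origin although it does not name it.

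**Step 2: what if every form were read from the left?** Since s_left = L - s_right, any difference becomes (L - a) - (L - b) = -(a - b). Standard deviations are unchanged, so t statistics change sign only. Ranks are reversed, and paired differences change sign. All four two-sided p-values therefore stay the same.

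A made-up data set confirms this. It assumes 18 per arm, baseline mean 60 mm and SD 15, average falls of 30 and 15 mm, and noise SD 10.

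| Quantity | From the right | From the left |
|---|---|---|
| Within-group change, active arm | -29.6 mm | +29.6 mm |
| Post-treatment group difference | -8.4 mm | +8.4 mm |
| t statistic | -1.63 | +1.63 |
| t test p | 0.111 | 0.111 |
| Mann-Whitney p | 0.141 | 0.141 |

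The paired t and Wilcoxon p-values in the active arm also agree between the two readings. These are not trial data.

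**Step 3: what if only some forms were read from the wrong end?** If a share q is misread regardless of the score, a group mean m becomes (1 - q)m + q(L - m) = qL + (1 - 2q)m. With the same q in both arms the term qL cancels, and a true difference d becomes (1 - 2q)d. For an assumed d = 20 mm:

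- q = 0.10: 0.80 × 20 = 16 mm
- q = 0.20: 0.60 × 20 = 12 mm
- q = 0.25: 0.50 × 20 = 10 mm
- q = 0.50: 0 mm
- q = 1: -20 mm

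If q differed between arms, qL would not cancel and the simple factor would not apply. Every q above zero is hypothetical.

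**Step 4: how many records are involved?** There are 36 × 2 = 72 scores. The Outcomes section says that all measurements were taken three times and averaged; if that includes the VAS, there are up to 36 × 2 × 3 = 216 marks.

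**The case for a change.** The strongest case for a change is that the rule turning a mark into a number is left to inference, for the measure on which a pain trial most depends. The orientation sentence cannot be dismissed as wholly generic, because its parenthesis ties it to this study. The NDI is given item scoring, range and direction, and the SF-36 its endpoints and direction, so the VAS is the less fully defined scale. A full reversal might be noticed, but a partial one could pass unseen among 36 participants. One sentence would settle the matter.

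Part of this stands: neither the measuring end nor the length of the form used is written down, and a reader cannot tell whether the orientation sentence describes the printed form or is a drafting slip. The rest carries less weight. Direction need not be inferred by analogy, because it is stated outright. Nothing points to forms being read in different ways: assessments were made by a single experienced clinician, and the questionnaires were completed under supervision, although supervision is described only for the pre-treatment forms. A complete reversal would set the VAS against the NDI and the pressure threshold from the same assessments, although the document describes no such cross-check. The harm requires the team to score against its own rule and not notice.

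**Conclusion.** The concern does not call for a change. Line orientation and scoring direction are separate properties, and the two stated here are compatible when the score is the distance from the no-pain end. The contradiction arises only if a left-hand origin is added, and the document supplies none. A team that applies the stated rule obtains a sound VAS result, and no design feature, test or sample size depends on the missing detail.

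Under a consistent misreading, the damage is limited to the sign: the size of every difference and the two-sided p-values are unaffected. This holds for any line length, provided the tests are two-sided. The dilution factor (1 - 2q) is correct arithmetic for equal misreading in both arms, but it measures an event for which there is no evidence. Confirming the measuring end against the forms is ordinary data handling for 72 scores, or up to 216 marks, and needs no amendment. The document does not show that any form was mis-scored. Evidence that the forms had been scored from the left, or inconsistently, would alter this conclusion.

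### The between-group comparison is an unadjusted t or Mann-Whitney test: valid, but it leaves unused a baseline measured for every outcome, where ANCOVA would probably gain precision for one degree of freedom

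*Combined protocol and SAP*

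**What the plan says.** Under Outcomes, VAS, NDI, SF-36, range of motion and pressure pain threshold "were evaluated blindly by an experienced sports medicine clinician before and after the treatment", so each has a baseline value and a post-treatment value. Under Treatment, the two randomised arms are described: "capacitive resistive therapy and exercise were applied to one group, and placebo (sham) therapy and exercise were applied to the other group".

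The Statistical Analysis Plan section states what is compared: "Evaluations were made both within the group before and after treatment (TO) and also for intergroup before and after treatment". For comparisons between groups it gives a parametric rule: "Student t Test was used for group comparison of variables with normal distribution". The remaining variables get a rank test instead: "Mann Whitney U test was used for group comparisons of non-normally distributed variables". The paired t and Wilcoxon tests are kept for dependent samples. They link before to after, but only inside one arm. The significance level is 0.05. Neither ANCOVA, a covariate, a change score nor a group-by-time term appears anywhere in the document.

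**The concern.** The most natural reading of the sentence is two separate between-group tests per outcome, one before treatment and one after. The first tests for a difference between randomised groups at baseline, where any difference is due to chance, so its p-value informs nothing. The second ignores the baseline value.

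The sentence can also be read as a between-group comparison of before-to-after change. That uses the baseline by subtraction, but usually less efficiently than regression adjustment. The plan does not say which value is tested.

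At stake is precision in a small trial: a real effect is more likely to be missed, and the interval around the estimate is wider than it need be. In addition, the unadjusted estimate moves with any chance baseline imbalance in that outcome, and the plan provides no adjusted estimate to set beside it.

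**Working it through.** The plan gives no sample-size or power calculation, so there is no figure of its own to reproduce.

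**Inputs from the document.** Total of 36 participants (Material and Methods), two arms, block randomisation, significance level 0.05.

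**Assumptions.** 18 per arm (the ratio is not stated), two-sided test, normal data with equal SDs, no dropout, and an illustrative true effect of 0.7 SD. The baseline-to-post correlation, rho, is not given, so 0.3, 0.5 and 0.7 are shown. The ICCs quoted under Outcomes describe measurement reliability, not correlation across three weeks of treatment, and are not used for rho.

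**Variance of the estimated effect, relative to a test of post-treatment values.**
- Post-only: 1, with 34 df.
- Change score: 2(1 − rho), with 34 df: 1.4, 1.0, 0.6.
- ANCOVA: (1 − rho²) × 33/32, with 33 df: 0.938, 0.773, 0.526. The factor 33/32 is the cost of estimating the slope.

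**Power.** The noncentrality is 0.7 / √(V × 2/18), where V is the relative variance. For post-only it is 0.7 / 0.333 = 2.10; for ANCOVA at rho 0.5 it is 2.10 / √0.773 = 2.39. Power comes from the noncentral t distribution.

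| | rho 0.3 | rho 0.5 | rho 0.7 |
|---|---|---|---|
| Power, post-only | 53% | 53% | 53% |
| Power, change score | 41% | 53% | 75% |
| Power, ANCOVA | 56% | 64% | 80% |
| 80%-power effect (SD), post-only | 0.96 | 0.96 | 0.96 |
| 80%-power effect (SD), change score | 1.14 | 0.96 | 0.74 |
| 80%-power effect (SD), ANCOVA | 0.93 | 0.85 | 0.70 |
| Mean 95% CI half-width (SD), post-only | 0.67 | 0.67 | 0.67 |
| Mean 95% CI half-width (SD), ANCOVA | 0.65 | 0.59 | 0.49 |

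The half-widths come from simulation with 200,000 trials per cell, which also reproduced the powers to within about 0.2 percentage points.

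**Where the gain stops.** ANCOVA and post-only have equal variance when (1 − rho²) × 33/32 = 1, that is at rho = √(1/33) = 0.174. ANCOVA and change score are equal when (1 + rho) × 33/32 = 2, that is at rho = 64/33 − 1 = 0.939. In the worst case against post-only, rho = 0, ANCOVA variance is 3.1% higher and power falls from 53.2% to 51.9%.

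**Validity.** With no true effect, simulated rejection over all randomisations was 5.0% to 5.1% for all three methods.

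**Chance imbalance.** The SE of the baseline difference is √(2/18) = 0.333 SD, so the chance of an imbalance above 0.5 SD is P(|Z| > 1.5) = 13% per outcome. Simulated rejection with no true effect, given an exact imbalance:

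| Imbalance, method | rho 0.3 | rho 0.5 | rho 0.7 |
|---|---|---|---|
| 0.5 SD, post-only | 6% | 8% | 10% |
| 0.5 SD, change score | 9% | 8% | 7% |
| 0.5 SD, ANCOVA | 5% | 5% | 5% |
| 0.25 SD, post-only | 4.6% | 3.8% | 2.4% |
| 0, post-only | 4.1% | 2.5% | 0.7% |

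The unadjusted test rejects too often when the arms start apart and too seldom when they start level. The two average out to 5%.

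**The case against.** - **This is a preference for efficiency, not an error.** A t or Mann-Whitney test of randomised groups is legitimate, and nothing in the document contradicts it. This stands, and it is why the point is a recommendation and not a claim of invalidity.
- **The gain is assumed.** Rho, SD, effect size, allocation ratio and sidedness are all absent, and at the 0.7 SD effect the gain over post-only runs from about 2.5 points at rho 0.3 to 27 points at rho 0.7. The documents cannot place the trial in that range. This stands, but the trade is lopsided: the worst loss against post-only is about one point of power.
- **A change-score reading does use the baseline.** True. ANCOVA still gains 15, 11 and 5 points on that reading over the range shown.
- **A 0.5 SD imbalance is the unfavourable case.** Fair: about 55% of randomisations fall within 0.25 SD, where the unadjusted test is conservative. The imbalance figures show sensitivity to baseline, not overall inflation of false positives.
- **ANCOVA has assumptions, and more analyses mean more choice.** Linearity and a common slope may be strained by bounded VAS and NDI scores with about 18 per arm, and the normal-data figures do not measure the gain for outcomes sent to Mann-Whitney. This stands as a reason to check residuals and to fix one lead analysis per outcome.
- **It may be too late.** The section is in the past tense and the document is dated 17.03.2020. That limits the status of the change, as set out under the fix, but not its value.

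**Conclusion.** The concern holds. The only between-group analysis stated is unadjusted, it leaves the tested value unclear, and on its plain reading it makes no use of the baseline. The plan is inefficient, not invalid.

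Under the stated assumptions, ANCOVA cuts the variance against a post-only test by 6%, 23% and 47% at rho 0.3, 0.5 and 0.7. At rho 0.5 that is worth about 47 participants instead of 36 (36 / 0.773 = 46.5). Confidence is high that the plan lacks an adjusted analysis and that ANCOVA is the better default. The size of the gain depends on a correlation the documents do not give. The change should be made; the trial's conclusions do not fail without it.

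**What to change.** For each outcome, make the between-group analysis an ANCOVA of the post-treatment value on treatment group, with the baseline value of the same outcome as covariate. Report the adjusted mean difference, capacitive-resistive minus sham, with its 95% CI. Present baseline values descriptively and drop the between-group test of them. Check residuals, and give a rank-based ANCOVA as a sensitivity analysis in place of choosing the test by Shapiro-Wilk.

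The cost is one degree of freedom and a dated amendment. No participants, visits or measurements are added, and the SPSS package already named can run it.

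The amendment must state what had been seen when it was made. Inclusion ended on 1 March (year not given; 2020 assumed), and on the schedule "The sessions were continued for 3 weeks with an interval of 24-48 hours". If the last participant started on 1 March, three full weeks end about 22 March, after the document date. Counting instead nine intervals between ten sessions, 9 to 18 days, gives about 10 to 19 March, which straddles it. The documents therefore do not show whether outcome data had been examined by group. If they had, label the ANCOVA post hoc and report it alongside the tests originally planned.

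### The between-group analysis is an unadjusted test at 0.05: no treatment difference with a confidence interval is specified, and the baseline values collected for every outcome are not used in it.

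*Combined protocol and SAP*

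**What the plan says.** The analysis plan is a single paragraph under Statistical Analysis Plan at the end of the document.

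- Summaries of numerical variables: "Descriptive statistics of the numerical variables in the study are given as mean, median, min-max, standard standard deviation".
- Between groups: "Student t Test was used for group comparison of variables with normal distribution"; where normality fails, a Mann-Whitney test takes its place.
- Within groups: "For dependent groups, Paired t Test was used for mean comparisons and Wilcoxon test was used for median comparisons".
- Criterion: "In calculations, 0.05 was taken as the level of significance".

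The same paragraph says that intergroup evaluations are made both before and after treatment. The Outcomes section says that VAS, NDI, SF-36, range of motion and pressure pain threshold are all measured at both times, so every outcome has its own baseline value.

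On size and allocation, Material and Methods gives the total ("Thirty six volunteers with active myofascial trigger points in the upper trapezius and neck were included") and the method ("The patients were divided into two groups by a physician who did not participate in patient evaluation using the block randomization method"), but not the numbers per arm. No section names a between-group difference, a confidence interval, an adjusted analysis, a worthwhile difference, or a basis for the sample size.

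**The concern.** This is a sham-controlled efficacy trial in which both arms also exercise. Change within an arm therefore mixes the therapy with exercise, natural course and regression to the mean. Only the active-minus-sham difference isolates the therapy, and the plan tests that quantity without saying that it will be estimated with its uncertainty.

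Two things are lost.

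1. **Interpretation.** In a trial of this size a p-value above 0.05 is compatible with no effect and also with a large one. A p-value below 0.05 does not say how small the benefit might be. The interval answers both questions, and the plan does not call for it.
2. **Precision.** The after-treatment comparison ignores the patient's own starting value, which is usually a strong predictor of the later score. Using it costs nothing, because it is already measured.

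Testing the arms against each other before treatment does not make up for this. Under randomization any pre-treatment difference is due to chance, so that p-value informs no decision. Adjustment deals with the imbalance directly.

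**Working it through.** The plan gives no power or precision figure, so there is none to reproduce. Results are in SD units because the documents give no SD.

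**Inputs**

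| Input | Value | Source |
|---|---|---|
| Total patients | 36 | Material and Methods |
| Split | 18 and 18 | assumed; the ratio is not stated |
| Significance level | 0.05 | Statistical Analysis Plan |
| Sidedness | two-sided | assumed; not stated |
| Before-after correlation r | 0.5 and 0.7 | assumed |
| True effect | 0.5 and 0.8 SD | assumed |

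**Step 1: unadjusted 95% interval.** Half-width = t(0.975, 34 df) × √(1/18 + 1/18) = 2.032 × 0.333 = 0.677 SD. It is 0.678 SD at 17 and 19, and 0.682 SD at 16 and 20, so the exact split hardly matters. With only 15 per arm analysed it would be 0.748 SD.

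**Step 2: what a non-significant result could look like.** An observed difference of 0.4 SD gives t = 0.4 / 0.333 = 1.2 and p = 0.24. Its 95% interval is 0.4 ± 0.68, or −0.28 to 1.08 SD. At p = 0.50 the difference is 0.23 SD with interval −0.45 to 0.90 SD. Both results include zero and also effects of 0.9 SD or more.

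**Step 3: power of the unadjusted t test.** From the noncentral t with 34 df and noncentrality d / 0.333 = 3d:

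- d = 0.5: power 0.308, so about 69% of such trials are non-significant.
- d = 0.8: power 0.645, so about 35% are non-significant.
- 80% power is reached only at about d = 0.96.

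**Step 4: gain from baseline adjustment.** ANCOVA reduces the residual SD by the factor √(1 − r²) and costs one degree of freedom. Approximate half-width = t(0.975, 33 df) × √(1 − r²) × √(2/18), with t = 2.035:

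- r = 0.5: 2.035 × 0.866 × 0.333 = 0.587 SD; simulated mean 0.593 SD.
- r = 0.7: 2.035 × 0.714 × 0.333 = 0.484 SD; simulated mean 0.49 SD.

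The simulated values are slightly larger because they include chance baseline imbalance. Against 0.677 SD, the interval is narrower by 1 − 0.593/0.677 = 12% at r = 0.5 and by 1 − 0.49/0.677 = 28% at r = 0.7.

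**The case against.** A reader might draw three stronger conclusions from this plan. The documents do not support them.

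- *That the trial cannot tell no effect from imprecision.* Means and SDs are planned for all numerical variables. If they are given by arm, which is a reasonable inference though not stated, a reader can rebuild the unadjusted after-treatment difference and its interval. A baseline-adjusted interval cannot be rebuilt this way, nor can one for change unless the SD of change is reported.
- *That the Mann-Whitney route yields no effect size.* Medians are planned without exception for non-normal variables, so a difference in medians can be read off. What is missing is an interval, or a shift estimate that matches the test.
- *That the sponsor will read p > 0.05 as no difference.* The plan states a significance level and nothing about how a non-significant result will be interpreted. Nor does a short plan's silence show that no interval will be reported.

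Other objections carry some weight. The 69% figure depends on a true effect of 0.5 SD; at 0.8 SD a non-significant result is the less likely one. An interval reveals imprecision but does not reduce it, so the power figures bear mainly on sample size. The documents also define no worthwhile difference and name no primary outcome. Intervals across many outcomes leave multiplicity untouched.

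Finally, the sentence on intergroup evaluation might be taken to mean a comparison of changes, which would use the baseline. It does not say so; the natural reading is a test at each time point. Even on that reading the half-width would be 0.677 × √(2(1 − r)): 0.68 SD at r = 0.5 and 0.52 SD at r = 0.7, both wider than under ANCOVA.

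What stands is the omission of a specified estimate with its interval, and the unused baseline.

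**Conclusion.** The point holds as a gap in the specified between-group analysis, and it should be corrected. The planned tests are valid, but the plan does not commit to estimating the treatment difference with its uncertainty, and it leaves available precision unused. On the assumptions above, the unadjusted interval is about ±0.68 SD, and adjustment would bring it to about ±0.59 or ±0.49 SD depending on r. Power of the planned t test is roughly 31% to 65% for true effects of 0.5 to 0.8 SD.

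The omission and the unused baseline follow from the text alone. The sizes depend on an 18:18 split, two-sided testing, approximate normality, and assumed values of r and the true effect. The evidence does not show that the trial is uninterpretable or that a null result will be misreported.

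**What to change.** In the Statistical Analysis Plan:

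1. For each outcome, make the between-group analysis the active-minus-sham difference in after-treatment score, adjusted for that outcome's baseline by ANCOVA, with its 95% confidence interval.
2. Base the conclusion on this estimate and interval, not on p < 0.05 alone. An interval that includes both zero and an effect the sponsor would regard as worthwhile should be called inconclusive. The sponsor would need to state that effect, since the documents do not.
3. Where a rank test is shown, give the Hodges-Lehmann shift with its 95% interval.
4. Show pre-treatment values by arm descriptively, without intergroup p-values.

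The plan is written in the past tense. If results have already been seen, the change should be dated and described as added afterwards.

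**Cost:** a little extra analysis in standard software, with no new data and no change to trial conduct. The stated conclusion may become more cautious. Reporting the interval shows the imprecision that comes with 36 patients; only the baseline adjustment reduces it.
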